10.2. Method of analysis

The overarching goal of this pilot study is to assess the feasibility of a growth screening programme. We are guided by Bowen's framework for feasibility studies, in which three key questions for feasibility are presented.¹⁸ These are: *Can it work? Does it work?* and *Will it work?* In this study we focus largely on the first question, can it work, and seek to provide some preliminary data on the second and third questions. Bowen's areas of focus for feasibility studies informs how we will answer these questions:

Can it work?

Acceptability: Focus groups with parents and health visitors will provide information on the acceptability of growth screening (see Qualitative Analyses, below). We will also examine ongoing study participation (retention rate).

Demand: The uptake of invitations to participate in the study (response rate), as well as uptake of the screening mobile phone app will provide data on demand for growth screening.

Integration: We will test integration into current health visiting systems by assessing the success of data linkage with NCMP, the proportion of parents who consent to NCMP data linkage, and through focus group interviews with health visitors.

Does it work? Will it work?

Below we outline how we seek to provide evidence for limited-efficacy testing, to gain an initial understanding of whether the growth screening algorithm is able to identify children for further clinical investigation. Acceptability, demand and integration are also interwoven into the data analysis strategy throughout.

Aim 1

We will employ an algorithm based on previous methodology, using variables individually and in combination, after checking for co-linearity. Different cut-off values will be chosen and the proportion of the population judged to have linear growth failure estimated for each cut-off. We will then examine the detection rate for each cut-off by applying it to data from ~200 local children treated in the specialist paediatric endocrinology centre with known growth disorders e.g. Growth Hormone Deficiency (GHD), Turner Syndrome (TS) and Small for Gestational Age without catch-up growth (SGA). Consent will be obtained retrospectively from these patients and their parents/carers to link their routinely obtained clinical data (diagnosis, age at diagnosis, height and parental height) to previously height data obtained at school entry via the NCMP. To do this linkage, the hospital clinical data (and the associated NHS number or other identifiers) will be shared with NHS England. This will allow us to calculate sensitivity-and-specificity algorithm cut-offs for the detection of these conditions. This will enable a trade-off between detection rate (sensitivity) and the false positive rate (1-specificity) to be evaluated. Additionally, the time elapsed from the first abnormal screening result until the clinical diagnosis of growth hormone deficiency will be related to the cut-off values.

The outcomes for Aim 1 are age of identification of stunting (which will be reported but the study is not powered to detect age of diagnosis); feasibility of measuring children in the community; the percentage of children referred; the percentage of children found to have underlying medical conditions; and the feasibility, acceptability and inter-test variability of a smartphone app and stadiometer height measures.

The algorithm will be applied to measures collected from each child at each visit, with children who are identified by the algorithm as being in the bottom 2% for height or

growth being referred to clinic for further investigation. The proportion of children with complete observations, including height at three time points and parental height, will be compared to the proportion of children with fewer observation points or missing parental height. Descriptive statistics will be reported: the number and percentage of children found to be stunted and their characteristics (height, gender, age, socio-demographic factors). We will also report the number of children referred to clinic, attending clinic and found to have underlying medical conditions. The age at which each condition is identified will be reported and compared to the average age at diagnosis.

Height data collected by parents using a smartphone app will be analysed. The number of parents consenting to use of the smartphone app and reporting one or more height measurements through the app will be reported. The number of time points at which parent's upload smartphone measured heights will also be reported. Inter-rater reliability between parent-measured height using the smartphone app and Health Visitor measured height using a stadiometer will be assessed using Gwet's Agreement Coefficient.¹⁹

Aim 2

All children will undergo a developmental assessment in the community, conducted by a health visitor with input from the child's parent, as part of standard care (ASQ-3 questionnaire). A subset of 150 children will, in addition, have a gold standard developmental assessment conducted by a child psychologist using the GMDS, which measures gross motor, fine motor, social, language, visual-spatial and practical reasoning skills.

Data on socioeconomic circumstances will be used to model the probability of a child's risk of developmental delay or sub-threshold delay on the ASQ-3 (n=600) and GMDS (n=150). Poor growth (assessed by the algorithm) will then be included in these models to assess whether model fit is improved, and whether poor growth contributes to the predictive power of socioeconomic variables to predict developmental delay.

Concurrent validity of the ASQ-3 and GMDS will be assessed. Each measure will be used to assess whether the participant has any degree of developmental delay, based on measure-dependent cut offs. The degree of agreement will be assessed using Cohen's kappa, and interpreted using existing guidelines, where a kappa value of >0.4 reflects moderate agreement, and a kappa of >0.6 reflects substantial agreement.²⁰ The GMDS will also be used as a gold standard child development measure to assess the performance of the ASQ-3. Sensitivity and specificity will be calculated to assess the ability of the ASQ-3 of identifying children identified as having a delay by the GMDS.

The outcomes for Aim 2 are the correlation between the ASQ-3 and the GMDS; and the change in sensitivity with the addition of anthropometric and developmental data to an existing vulnerability index.

Qualitative analyses

To further our understanding of the acceptability of the proposed screening programme, we will conduct two focus groups with parents participating in the study, as well as one focus group with health visitors. The transcribed data from the focus groups with caregivers and health visitors will be used to generate coding categories and will be analysed using NVivo, using thematic analysis.

11. Ethics

Research Ethics Committee approval will be sought. This is not a trial and there is no intervention which could result in direct harm to participants. However, there are potential indirect harms related to the study. We will aim to mitigate these as far as possible and will include detail of these potential harms in the patient information and informed consent procedures.

Firstly, the study will involve collecting sensitive data, which if handled incorrectly could lead to identification of individual children or groups of children. The study procedures to de-identify or pseudo-anonymise children will reduce the risk of identification of individuals. The potential for 'group harm', in which a particular subpopulation (e.g. by area, ethnicity or gender) are stigmatized because of study findings, such as the finding of high prevalence of growth failure, will be minimized in publications and dissemination of study findings, by not releasing results relating to small areas.

An identification of short stature, faltering growth or delayed development (and subsequent referral for specialist care) could result in distress for children and their families and could lead to stigma. We will include information about stigma and discuss this with caregivers as part of the informed consent procedures. Further, if we identify issues with growth and/or development, children will be referred earlier than would have happened without their involvement in the study. Children will be immediately referred to a paediatric growth or community development clinic and as such will be provided care, support and if appropriate treatment for relevant conditions.

We will be providing vouchers worth £15 for the baseline visit as compensation for time spent during participation in the study. These are not intended as rewards for participation, but we are aware of the possibility of these payments leading to coercion. Research staff will undergo Good Clinical Practice and ethics training and will be careful to avoid coercion in recruitment procedures.

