6.1. Primary objective

Pilot an automated growth-screening algorithm in east London.

Within the primary objective we aim to test four hypotheses:

- **1.** Health visitor monitoring of child height using an automated growth-screening algorithm is feasible and is acceptable to health visitors and caregivers.
- **2.** Referral of children to a paediatric growth clinic has high uptake and identifies growth problems in pre-school age children.
- **3.** An additional height measurement by the child's health visitor or at the preschool booster immunisation appointment at the child's GP practice is feasible and acceptable.
- **4.** Linkage of children's health visitor data to their height measurement as part of the NCMP is feasible and is acceptable to caregivers.
- **5.** A smartphone app is feasible and acceptable for caregivers to use to measure their children's height at pre-school age, and there is acceptable inter-test variability between the smartphone measurement and the clinician measurement with a stadiometer.

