6.4. Secondary endpoints

• Linear growth trajectory

This will be assessed by child height measurements at age 2-2.5 years, age 2.5-3.5 years, and age 4-5 years, in combination with target parental height. Parents who make use of the app will provide additional longitudinal growth measurements between age 2-5 years. All measurements will be entered into an algorithm, developed using data from two longitudinal UK cohorts (Millennium Cohort Study and Born in Bradford), which will identify children with poor linear growth based on absolute height, growth velocity and distance from target height.

• Child development at age 2-2.5 years.

This will be assessed using the ASQ-3 questionnaire and the GMDS, as described above.

7. Study population

This study will enrol a cohort of 630 children living in Tower Hamlets into a pilot screening programme at age 2.0-2.5 years and apply a growth-screening algorithm to identify children with poor growth. Children will be selected randomly from health visitor records in Tower Hamlets to ensure a representative sample, based on the inclusion and exclusion criteria outlined in section 7.1 and 7.2. We will include all children whose caregivers are willing to provide written informed consent to i) have a height/weight measurement (+/- a developmental assessment) together with a baseline questionnaire undertaken at age 2.0-2.5 years (by the health visitor) and a repeat weight/height measurement at age 2.5-3.5 years (either by the health visitor as an additional visit or by the GP surgery at the time of pre-school vaccinations); ii) undergo longitudinal growth screening by the parent using an app which measures a child's height; and iii) have the child's identifiers sent to Tower Hamlets Local Authority in order to access their weight/height measurement undertaken at school at age 4.0-5.0 years through the NCMP programme, to prove feasibility of data linkage. We will work in partnership with Tower Hamlets GP Care Group to identify a representative sample of children from the borough based on health visitor lists, to ensure we minimise bias and include even the hardest-to-reach participants.

We will also conduct a secondary analysis of a clinical sample of ~200 children with confirmed growth disorders e.g. Growth Hormone Deficiency, growth failure associated with small for gestational age and Turner syndrome (clinical sub-study).

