9.3 Informed consent

Informed consent will be taken by the study health visitor in a confidential setting (within a children's centre or the child's house) using e-consent on the REDCap database, which includes the questions on the study informed consent form (Form 4). If necessary, consent can be taken on paper using the same form and will still be considered valid. This will take place either prior to the first measurement/development assessment at age 2-2.5 years or on the day of this assessment. An electronic signature will be taken; in addition to a tick box and declaration, permitted forms of electronic signatures will include a stylus or finger drawn signature or a typed name. The health visitor will explain all study procedures, risks and benefits and confidentiality considerations. The study health visitor will explain that the project involves two assessments by health professionals, 6-12 months apart (one at the 2-2.5 year health visitor contact and one undertaken either by the GP surgery at the preschool booster immunisation appointment, or by the health visitor). In addition, as per standard care all children will have their development assessed by the health visitor using the parent-reported ASQ-3 assessment. Parents will also be invited to download a smartphone app and to measure their child's height at 3 timepoints, each time on the same day as the child's height is measured by a health professional (health visitor, GP practice nurse, school nurse). Caregivers will also be asked for consent to health visitors' collection of data on past medical history from children's primary care records and linkage of any relevant diagnoses or medications to the children's study data. It will also be made clear that there will be data linkage with the NCMP programme through Tower Hamlets Local Authority, which involves sharing identifiers (NHS number) if they are happy to provide consent for this to occur. Caregivers can opt out of this data linkage and their child can still be included in the internal study. Caregivers will be made aware that they will be provided with the child's growth measurements and a summary of their growth pattern, and that children with severe growth failure will be contacted and referred to the paediatric endocrinology service, and children with significant developmental concerns will be referred for further assessment through existing NHS referral pathways. In addition to data entry onto the NHS system, the caregivers will be made aware that their child's anthropometric and developmental data, and the parental heights will be recorded in a research database (REDCap) by the health visitor. Caregivers will be asked for consent for routine clinical data collected in the clinic (such as any diagnoses made by the endocrinologist) to be linked with the child's data in the study. [name] is a member of the study team and

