Clinical sample linkage information sheet for carers/parents (Form 24)	Information leaflet for clinical sample NCMP linkage	Study team
Clinical sample linkage information sheet for patient aged 16 or over (Form 25)	Information leaflet for clinical sample NCMP linkage	Study team

Baseline visit (age 2.0-2.5 years):

At the baseline visit, data will be collected using CRF1 (Baseline visit). Demographic data will be collected from the caregiver. Caregivers will be asked to have the personal child health record (Red Book) available, from which will be transcribed: birth weight and length (if available) and any previous measurements of height, weight and head circumference. We will also collect data on gestation and growth on antenatal scans, feeding difficulties including any previous interventions from dietetics or paediatrics, chronic health conditions and any hospital attendances/admissions. The child's height will be measured to the nearest 1mm using a stadiometer according to an SOP. The child's weight will be measured to the nearest 100g using a stand-on scale according to an SOP. The accompanying parents will have height measured using the same methods; if either parent is absent, an estimate will be made of their height based on parental recall. If both parents are not present (i.e. the child is cared for by different family member), we will attempt to contact the parents to record their reported heights. If the child is not in contact with their biological parents, we will not make further attempts to contact family members and will record this as missing data. Health visitors will support caregivers to download a smartphone growth application and demonstrate how to use it. Caregivers will be invited to take the first smartphone measurement at this point. The app converts height data from the camera image to a numerical figure, and this will be transferred to a secure central server with additional relevant demographic data (e.g. gender, ethnicity, weight, date of birth and parents' heights) and an anonymous identifier in GDPR-approved secure space. Each participant will have an anonymised unique identifier. No patient images / names will be transferred. The smartphone app has existing ethical approval (IRAS project ID: 286683; REC reference: 21/WM/0032).

Follow-up visit 2.5-3.5 years

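### App and stadiometer heights are both numerical, yet the only stated agreement analysis is Gwet's Agreement Coefficient, which gives neither bias nor limits of agreement in cm

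*Protocol*

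**What the plan says.** Hypothesis 5 under the primary objective (section 6.1) includes the claim that "there is acceptable inter-test variability between the smartphone measurement and the clinician measurement with a stadiometer". Section 10.2 lists the "inter-test variability of a smartphone app and stadiometer height measures" among the Aim 1 outcomes.

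Both measurements are numerical. In the baseline visit description under the schedule of study interventions, the child's "height will be measured to the nearest 1mm using a stadiometer according to an SOP", and "The app converts height data from the camera image to a numerical figure". Section 9.3 asks parents to use the app at three time points, "each time on the same day as the child's height is measured by a health professional".

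For the analysis, section 10.2 says, under the label of inter-rater reliability, that Health Visitor "measured height using a stadiometer will be assessed using Gwet's Agreement Coefficient". Its other app analyses are counts of consent, use and time points. The synopsis repeats the aim without a method. The protocol names no mean difference, SD of differences, limits of agreement or intraclass correlation for these heights.

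**The concern.** Whether variability between two height methods is acceptable is a question about the size and direction of error in cm. Gwet's coefficient has no units. Its unweighted form treats readings 1 mm apart as full disagreement. Its weighted forms accept interval scores and fall as error grows, but they merge systematic and random error into one value.

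The distinction matters here. Section 6.4 counts app heights as additional longitudinal measurements and states that "All measurements will be entered into an algorithm", which works on absolute height, growth velocity and distance from target height. A fixed app offset carries in full into a velocity formed from one app and one stadiometer reading. An offset can be calibrated out; wide random error cannot. The pilot is meant to inform a larger application, which would need to know which of the two it faces.

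**Working it through.** The protocol gives no figure on this point to reproduce. The check has two parts.

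**1. What the coefficient measures.** Gwet's coefficient is AC = (pa − pe)/(1 − pe). Here pa is the mean agreement weight over pairs. The chance term is pe = [T/(q(q − 1))] × Σπk(1 − πk), with q categories, T the sum of all weights and πk the average share of readings in category k. For a difference d and a range R of heights:

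- Unweighted: the weight is 1 if d = 0, otherwise 0. With 1 mm categories, exact matches are rare whatever the app's quality.
- Quadratic weights: the weight is 1 − (d/R)², so pa = 1 − MSD/R², where MSD = bias² + (SD of differences)². Bias and scatter enter only as a sum.

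**2. Illustration.** All inputs are assumptions, not protocol figures: 400 pairs at one visit, height SD 3.5 cm, stadiometer error SD 0.2 cm, heights rounded to 0.1 cm, 40 replicates, categories limited to observed values. Limits of agreement are bias ± 1.96 × √(0.2² + app error SD²).

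- (a) Accurate app, bias 0, error SD 0.3: SD of differences √(0.04 + 0.09) = 0.36; limits ±0.7 cm.
- (b) Bias 2 cm, error SD 1: SD of differences √(0.04 + 1) = 1.02; limits 2 ± 2.0, or about 0 to 4 cm; MSD = 4 + 1.04 = 5.04.
- (c) Bias 0, error SD 2.3: SD of differences √(0.04 + 5.29) = 2.31; limits ±4.5 cm; MSD = 5.33.

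| App | Mean difference, cm | 95% limits, cm | Unweighted | Linear | Quadratic |
|---|---|---|---|---|---|
| (a) | 0.0 | −0.7 to 0.7 | 0.10 | 0.95 | 0.997 |
| (b) | 2.0 | 0.0 to 4.0 | 0.00 | 0.67 | 0.91 |
| (c) | 0.0 | −4.5 to 4.5 | 0.01 | 0.71 | 0.91 |

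For height SD 3.0 to 4.0 cm, the quadratic value runs from about 0.89 to 0.93 for (b) and 0.90 to 0.93 for (c). The unweighted value for (a) stays at 0.10 to 0.11.

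Category handling also moves the result. Counting the empty 1 mm categories raises the quadratic values for (b) and (c) to about 0.95 each, and the linear values to about 0.74 and 0.78.

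The quadratic values for (b) and (c) agree because their MSDs are close (5.04 and 5.33). Yet in (b), 4/5.04 = 79% of the MSD is the squared offset. Removing that offset would leave limits of ±2.0 cm for (b), while (c) would stay at ±4.5 cm.

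**The case against.** - **The SAP may add to this.** The protocol does not say that the coefficient will be the only summary, and an unseen SAP could report differences in cm. That is possible, and the unstated weights and margin are not held against the protocol. The protocol does, however, name one specific statistic that does not suit the data, and an SAP that follows it would inherit the problem.
- **A weighted coefficient does separate good from poor apps.** This is true: linear weights give 0.95 against 0.67 and 0.71. What it does not do is say whether a poor value reflects offset or scatter, or how many cm are involved.
- **The scenarios are chosen.** Error SD 2.3 cm in (c) brings its quadratic value close to that of (b), and 0.91 is not a firm figure given its dependence on category handling. The match shows that two very different apps can score alike, not how often they will. The formula for pa shows why this can happen.
- **The stakes are limited.** This is a feasibility pilot, the primary endpoint lists only uptake of the app, and the comparison is part of one of five hypotheses. Because app readings are taken on the same day as a professional measurement, it is unclear whether an app error alone could change a referral. The raw pairs are kept, so limits of agreement can be calculated later. All of this stands and keeps the point at moderate weight. A margin chosen after the results are seen would nevertheless carry less conviction.

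**Conclusion.** The concern holds. The protocol fixes, for two numerical same-day heights, a unit-free coefficient that reports neither bias nor spread in cm under any weights, although its own hypothesis and Aim 1 outcome are about variability between the methods. In the illustration, the unweighted form scores an accurate app at about 0.10. The quadratic form gives about 0.91 (about 0.95 with empty categories counted) both to an app with a 2 cm offset and to an unbiased app with limits of ±4.5 cm. These values rest on the assumed height SD, error sizes, weights and category handling; the conclusion about the choice of statistic does not. The plan should be changed, but the point does not threaten the pilot's primary endpoint.

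**What to change.** In section 10.2, Aim 1, make the main app analysis the mean paired difference (app minus stadiometer) with 95% limits of agreement (Bland–Altman) in cm, with confidence intervals and allowance for repeated pairs per child. State in advance the margin in cm against which the limits will be judged. This alone cures the defect. Reporting by visit and in height SDS, with an intraclass or concordance correlation as a secondary summary, would be useful but is optional. Gwet's coefficient can be kept for agreement on a categorised result, such as flagged or not flagged by the algorithm.

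The cost is a little analysis work and agreement on the margin. Same-day pairs are already planned, so no extra data or visit procedure is needed. Precision should be adequate. If the SD of differences is 1 cm (assumed), 100 to 600 independent pairs give 95% confidence half-widths of 1.96/√n = 0.20 to 0.08 cm for the mean difference, and 1.96 × √(1/n + 1.96²/(2(n − 1))) = 0.34 to 0.14 cm for each limit.

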At each of the 3 measurements of height we will identify the 2-3% of children with the poorest growth, as categorised by the algorithm (based on parental height, child height, and child growth velocity), in whom prior studies show a high prevalence (30-40%) of medical disorders. We will contact parents of these children to offer referral to the paediatric endocrinology clinic at the Royal London Hospital. A member of the study team will call the parents to inform them and will write to the child's GP to request a referral into the Royal London Hospital clinic via the e-referral system. We will evaluate acceptability and feasibility of the screening and referral process, using parental and primary care staff questionnaires. We will evaluate uptake by calculating the proportions screened, referred, investigated in clinic and diagnosed with medical disorders. At the clinic, children will be assessed by a paediatric endocrinologist and will undergo routine medical evaluation for short stature, with appropriate follow-up.

Development sub-study (age 2.0-2.5 years):

A random sample of 150 children will also be invited to enrol in a sub-study to generate pilot data on the sensitivity of the parent-reported ASQ-3 to assess child development compared to a gold standard development battery, the GMDS, undertaken by a psychologist. These children will undergo a neurodevelopmental assessment during their routine health visitor visit of their motor, cognitive, language and social skills using a standardized test battery (GMDS) by a child psychologist. Using data from the ASQ-3 developmental assessments conducted at baseline and follow up visits by the health visitor, we will investigate relationships between growth and development and assess content validity of the ASQ-3 by comparing it with the GMDS.

[figure not shown]
Qualitative sub-study (following the 2-2.5 year visit)

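### Aim 2 tests whether growth adds to socioeconomic data only on a delay category; a pre-specified regression on the ASQ-3 and GMDS scores beside it would be a cheap improvement

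*Protocol*

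**What the plan says.** Protocol Section 10.2, Aim 2, gives one model for whether growth adds to socioeconomic data. Socioeconomic data will be used to "model the probability of a child's risk of developmental delay or sub-threshold delay on the ASQ-3 (n=600) and GMDS (n=150". The next step is: "Poor growth (assessed by the algorithm) will then be included in these models to assess whether model fit is improved". The same sentence goes on to ask whether poor growth helps to predict delay beyond the socioeconomic variables.

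For the comparison of the two instruments, the section says: "Each measure will be used to assess whether the participant has any degree of developmental delay, based on measure-dependent cut offs". It states no numerical cut-off and no expected prevalence of delay.

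One of the two listed Aim 2 outcomes is "the change in sensitivity with the addition of anthropometric and developmental data to an existing vulnerability index". Section 6.2 words the matching hypothesis as an increase in pick-up rate. The development sub-study text in Section 9.4 is broader: "we will investigate relationships between growth and development". No section describes a regression with the ASQ-3 or GMDS score as outcome.

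**The concern.** Aim 2 contains two questions. One is classification: does adding growth pick up more children with delay? That needs a delay status. The other is whether growth carries information about development beyond socioeconomic data, which Section 10.2 puts as an improvement in model fit. That question needs no cut. Putting it only to a category treats children just below and far below the threshold as alike, and does the same for all children above it.

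The pilot is meant to inform a larger application. If a real but moderate association fails to show in the fit comparison because the outcome was coarsened, growth may look less useful than the collected data could have shown. The GMDS set has only 150 children, so it has little information to spare.

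**Working it through.** **The plan's own figures.** The only power statement is for Aim 1 (Section 10.1: n=12, 5% versus 35%, 85% power). An exact binomial rule of at least 3 of 12 gives a one-sided error of 0.020 and power of 0.849, so that figure reproduces. It has no bearing on Aim 2, for which no power is stated and no stated figure is in dispute.

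**Inputs from the protocol.** n=600 (ASQ-3) and n=150 (GMDS). Section 10.2 refers "children who are identified by the algorithm as being in the bottom 2% for height or" growth, and other sections say 2-3%. If poor growth means that flag, it marks 0.02 × 600 = 12 to 0.03 × 600 = 18 children in the ASQ-3 set. In the GMDS set it marks 0.02 × 150 = 3 to 0.03 × 150 = 4.5, so 3 to 5 children.

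**Assumptions (none is in the protocol).** Two-sided 5% test; normal scores; a share p of children classed as delayed, taken as 10-25% with 40% as an extreme; effect sizes as shown.

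**Case 1: growth as a continuous measure.** For partial correlation r the test on the score has expected z of about λ = r√n / √(1 − r²), and power is Φ(λ − 1.96). Cutting a normal score at the p-th centile keeps a fraction E = φ(z_p)² / [p(1 − p)] of the information for a small effect, so λ becomes λ√E.

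- p = 0.10: 0.1755² / 0.09 = 0.342, √E = 0.585
- p = 0.25: 0.3178² / 0.1875 = 0.539, √E = 0.734
- p = 0.40: 0.3863² / 0.24 = 0.622, √E = 0.789

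| n, r | λ | Power on score | p = 0.10 | p = 0.25 | p = 0.40 |
|---|---|---|---|---|---|
| 150, 0.20 | 2.50 | 71% | 31% | 45% | 51% |
| 150, 0.25 | 3.16 | 89% | 46% | 64% | 70% |
| 600, 0.10 | 2.46 | 69% | 30% | 44% | 49% |

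Simulations with three socioeconomic covariates, p = 10-25%, comparing linear regression on the score with logistic regression on yes/no delay, agree:

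- n=150, r=0.20: 72-76% versus 34-44%
- n=150, r=0.25: 88-91% versus 47-67%
- n=600, r=0.10: 71-75% versus 32-46%

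Across formula and simulation the loss is roughly 15-45 points.

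**Case 2: growth as the 2-3% flag, n=600.** For a deficit of d SD in flagged children and flagged share f, λ on the score is d√[n f(1 − f)]. With d = 0.5 this is 0.5 × √11.76 = 1.71 at 2% and 0.5 × √17.46 = 2.09 at 3%, giving power of 40% and 55%. Simulated power, score versus yes/no:

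- d = 0.3: 17-26% versus 10-17%, a loss of 3-10 points
- d = 0.5: 40-53% versus 23-38%, a loss of 14-24 points
- d = 0.7: 70-87% versus 43-65%, with losses up to about 33 points

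**Case 3: the flag, n=150.** With d = 0.5, λ is 0.5 × √2.94 = 0.86 at 2% and 0.5 × √4.365 = 1.04 at 3%, so power on the score is only about 14-18%. Simulated for deficits of 0.3 to 0.8 SD, power is 7-39% on the score and 5-30% on yes/no. The loss is about 0-14 points, mostly under 8.

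**Three levels instead of two.** If none, sub-threshold and delay are kept as ordered levels, simulated power is at most 7 points above an any-delay yes/no outcome, and at most 3 points above it when growth is continuous. With continuous growth and mid-range power, most of the loss remains.

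**The case against.** The strongest reply is that Aim 2 is about classification. Pick-up rate, change in sensitivity and prediction of delay all need a delay status. A shift in mean score across the whole range does not show that more delayed children are detected, so a score regression answers a different question. This stands. It rules out replacing the delay models or making the score regression the main analysis.

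Second, a reader might infer that the plan loses some 10 to 40 points of power as it is written. The protocol does not support that. It gives no prevalence, effect size or Aim 2 power, and what it adds to the model is poor growth as assessed by the algorithm, which may be the 2-3% flag. With 3 to 5 flagged children in the GMDS set, a score model would not rescue that test.

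Third, the simulations assume a uniform shift, which favours the score. If instead 25-35% of flagged children have a 2 SD deficit and the rest none (n=600), the loss is 4-13 points at a 10-15% cut and 18-23 points at a 25% cut. The direction stands; the size is softer.

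Fourth, this is a secondary objective of a pilot, and the Section 9.4 wording leaves room for a score analysis that an analysis plan not shown here could contain. That limits the weight of the point. Even so, Section 10.2 itself fixes the outcome of the fit comparison as a category.

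**Conclusion.** The point holds as a cheap improvement, not as an error. The fit comparison in Section 10.2 is specified only on a category cut from graded scores, and this gives up information that the study will already have. Three conditions govern the size: how growth is entered, how common delay is, and how strong the association is. The loss is substantial with continuous growth and a moderate association, variable with the flag at n=600, and small with the flag at n=150, where power is low either way. It also shrinks towards zero when the true effect is very small or very large.

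Two stronger readings are tempting: that the category is itself a mistake, and that growth would be wrongly declared uninformative. The first fails because the stated targets need a category. The second fails because the protocol sets no significance test or decision rule for Aim 2 from which such a declaration would follow.

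**What to change.** In Section 10.2, Aim 2, add a pre-specified regression of the age-standardised GMDS score (n=150) and of the ASQ-3 scores (n=600) on the socioeconomic variables, first without and then with growth. Name it as the test of whether growth carries added information about development. Keep the delay and sub-threshold-delay models unchanged in role, as the analysis for pick-up rate and change in sensitivity.

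The cost is a wording change and one more model per measure, with no new data. The added results are in score units and do not themselves show better detection, so they must be reported beside the classification results. If ASQ-3 scores are skewed or limited by a ceiling, robust standard errors or an ordinal model will be needed.
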